The 4-week duration is chosen to capture adequate number of hypoglycaemic episodes. Most children are expected to experience at least 2 or more episodes per week.

'*Standard Hypo Rx First*' participants will use the standard hypo treatment⁵ (Hypoglycaemia treatment initiated with glucose level <3.9 mmol/L) for 4 weeks (Period 1)

'*Revised Hypo Rx First*' participants will start with revised hypo treatment plan (Hypoglycaemia treatment initiated at a lower glucose level for 4 weeks (Period 1)

During the study,

1. All participants will be encouraged to continue to wear their CGM during the entire duration of the study and be on closed loop therapy. Basal insulin delivery is suspended with prediction of hypoglycaemia with closed loop therapy. Hence, if the participant is not on sensor, participants should take standard hypo Rx.
2. Alerts
 - 2.1 Default (device in-built) urgent low alert at 3.0 mmol/L or 3.1 mmol/L will be **ON** for all participants during the study.
 - 2.2 Low alerts will be **ON**, in accordance with the glucose threshold of the study arm.
 - 2.3 Predictive low alerts are **optional**, as per choice of family.
3. Revised Hypo Rx
 - 3.1 Always institute hypoglycaemia treatment when symptomatic (irrespective of blood/sensor glucose levels)
 - 3.2 Always institute hypoglycaemia treatment when the revised glucose threshold of 3.6 mmol/L is reached.
 - 3.3 Always institute hypoglycaemia treatment when sensor glucose < 3.9 mmol/L with downward trend arrows on CGM, there is active insulin on board (post meal-bolus) or during and post exercise/activity.
 - 3.4 Hypoglycaemia treatment should not be instituted when sensor glucose is between 3.7 and 3.9 mmol/L and stable glucose levels on CGM and in closed loop therapy.
4. All participants will be advised to maintain a diary to log hypo events (glucose level, time and treatment given).

5. All participants will be provided an updated school management plan, when on the revised hypo Rx phase of the study,
6. During the entire study period, participants will be advised to ensure that they maintain optimal glucose levels as per recommendations for exercise and driving.

All participants will receive weekly review with email/phone calls by our team.

If time spent <3.0 mmol/L has doubled from baseline and/or is >1%, research staff (doctor and research diabetes educator) will review the participant to ensure 1) if they are 'true' hypoglycaemic events 2) explore the reason if 'true' hypoglycaemia.

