(c) whether and how participants are to be replaced
Participants will not be replaced

(d) the follow-up for participants withdrawn from the investigational product/trial treatment. If on the interventional arm, the participants will go back to standard care and will be followed up at their regular clinic visits.

6 Treatment of Participants

Description and justification for treatments, interventions or methods to be utilised

Revised Hypo Rx:

Product used is no different and is the glucose tablet or equivalent (available at pharmacies, multiple brands available) used by the participant for their standard hypoglycaemia management.

	Standard Hypo Rx	Revised Hypo Rx
Product name	Glucose tablet	Glucose tablet
Dose	0.15gm/kg glucose	0.15gm/kg
Route	Oral	Oral
Treatment instituted at	
 1. Glucose <3.9mmol/L 2. Symptomatic of hypo (Irrespective of glucose level) 	
 1. Glucose \leq3.6mmol/L 2. Glucose < 3.9 mmol/L with downward trend arrows on CGM, there is active insulin on board (post meal-bolus) or during and post exercise/activity. 3. Symptomatic of hypo (Irrespective of glucose level)
Study period	4 weeks	4 weeks

Permitted medications/treatments

Participants will continue their usual insulin management on AHCL and medications for any associated comorbidities for the duration of the study.

Monitoring of participant compliance

During the 'Revised Hypo Rx' arm of the study, weekly contacts will be made by the research team to monitor adherence and hypoglycaemia events during the study.

7 Assessment of Efficacy

Outcomes

Percentage time spent in clinically significant hypoglycaemia (sensor glucose levels < 3.0 mmol/L)

Efficacy assessment

This is a non-inferior study design, and the assessment will be based on the time spent in hypoglycaemia (SG < 3.0 mmol/L). Time spent in hypo < 3.0 mmol/L in intervention as compared to control group will be calculated and the upper bound of 95% CI will be compared to a pre-defined non-inferiority limit.

8 Assessment of Safety

Risks and benefits

The revised hypo Rx has the potential to increase the time spent < 3.0 mmol/L (on CGM) and increase the number of hypo events. However, this risk is mitigated by:

1. Using only users of closed loop therapy in the study. Closed loop therapy will suspend basal insulin delivery with *prediction of hypo* and will only resume insulin delivery with rising sensor glucose (as directed by the closed loop algorithm).

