2. Although the revised hypo treatment is to initiate treatment ≤ 3.6 mmol/L, treatment of glucose level < 3.9 mmol/L is recommended if there are downward trend arrows on sensor, active insulin on board and precedent activity/exercise. All families are educated on decision making with CGM trend arrows around hyperglycaemia/hypoglycaemia management.

The benefits to the participants are that they may achieve better glycaemic control with a reduction in overtreatment with hypoglycaemia.

Safety

- a. The sensor glucose levels of all study participants are available to participants in real-time which will enable them to take appropriate clinical action as required.
- b. Urgent low notification at < 3.0 mmol/L or 3.1 mmol/L is default (factory-set) and will be 'on' for all participants at all times. Carers will also have this feature on their phone as part of remote monitoring.
- c. Low notification will be set at 3.6mmol/L during the 'Revised Hypo Rx' phase and at <3.9 mmol/L for 'Standard Hypo Rx' phase.
- d. AHCL is dependent on the sensor glucose levels and basal insulin delivery will be adjusted based on sensor glucose readings. It is therefore expected to mitigate any significant risk of hypoglycaemia < 3.0 mmol/L.
- e. All participants are educated on the use of IM glucagon with severe hypoglycaemia (coma, convulsion, altered sensorium). This will be reviewed at Visit 1 as part of hypoglycaemia education.
- f. Establishment of a Data and Safety Monitoring Board
- g. All serious adverse events are to be recorded and reported to the investigators within 24hours.

Data and Safety Monitoring Board

A data and safety monitoring board (DSMB), consisting of an endocrinologist, a statistician and a clinical trial specialist, will be established to safeguard the interests of the trial participants and monitor the overall conduct of the study. The board will receive and review information on the progress and accruing data and provide advice on the conduct of the trial to the Principal Investigator and the Trial Management Group (TMG)*. The Principal Investigator and the TMG are required, under the DSMB charter for the study, to follow the DSMB's directions regarding the safety of the trial.

*The Trial Management Group, consisting of the research endocrinologist, the research nurse and the project manager, will be in charge of the day-to-day activities of the study.

Adverse event reporting

Adverse Event

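### In the revised phase, items 3.3 and 3.4 give opposite instructions for a stable closed-loop child at 3.7–3.8 mmol/L with active insulin or exercise

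*Protocol*

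**What the plan says.** The rules for the revised phase are in Protocol Section 4, During the study, item 3.

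- Item 3.1: "Always institute hypoglycaemia treatment when symptomatic (irrespective of blood/sensor glucose levels").
- Item 3.2: always treat once 3.6 mmol/L is reached.
- Item 3.3: "Always institute hypoglycaemia treatment when sensor glucose < 3.9 mmol/L with downward trend arrows on CGM, there is active insulin on board (post meal-bolus"), and the sentence goes on to add exercise, both during and afterwards, as a further alternative joined by 'or'.
- Item 3.4: "Hypoglycaemia treatment should not be instituted when sensor glucose is between 3.7 and 3.9 mmol/L and stable glucose levels on CGM" and the child is in closed loop. It names no exception and does not say which item takes precedence.

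The same triggers appear in three other places.

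- Section 6, treatment table, revised column: treat below 3.9 mmol/L "with downward trend arrows on CGM, there is active insulin on board (post meal-bolus) or during and post exercise/activity". The prohibition in item 3.4 is not in the table.
- Section 8, Risks and benefits, item 2: treatment below 3.9 mmol/L "is recommended if there are downward trend arrows on sensor, active insulin on board and precedent activity/exercise". Here the link is 'and', and only preceding exercise is mentioned.
- Section 16, acceptability questionnaire, item 5: it asks families about any other situation in which they would treat below 3.9 mmol/L. Arrows, a meal bolus and exercise are taken as already accepted reasons.

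On alerts, Section 8, Safety, item c says "Low notification will be set at 3.6mmol/L during the" revised phase. Section 4 leaves predictive low alerts to the family's choice.

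**The concern.** A stable trend does not exclude active insulin or recent exercise, and being in closed loop separates almost nobody, since closed-loop use is an inclusion criterion. So items 3.3 and 3.4 can apply to the same child at the same moment, one requiring treatment and the other ruling it out.

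The band matters because it is where the intervention lies. The standard phase treats below 3.9 mmol/L and the revised phase at 3.6 mmol/L or below, so the two thresholds differ only between these values. If item 3.3 governs, both phases treat the insulin and exercise situations alike. If item 3.4 governs, they differ. Section 8 presents early treatment in those situations as one of the reasons why the lower threshold is acceptable. A family or school that follows item 3.4 to the letter loses that protection.

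**Working it through.** The protocol states no figure on this point, so there is none to reproduce. The check is one of logic, with one subtraction at the end. It assumes that sensor glucose *g* is shown to 0.1 mmol/L and that the child is in closed loop.

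**Step 1. Write the two rules as conditions.**

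- Item 3.3, treat: *g* < 3.9 and (downward arrow or active insulin or exercise).
- Item 3.4, do not treat: 3.7 ≤ *g* ≤ 3.9 and stable trend.

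**Step 2. Find the overlap.** Both hold when 3.7 ≤ *g* < 3.9, the trend is stable, and there is active insulin or exercise. At 0.1 resolution this means 3.7 and 3.8.

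| *g* (mmol/L), stable, active insulin or exercise, no symptoms | Item 3.2 | Item 3.3 | Item 3.4 | Result |
|---|---|---|---|---|
| 3.6 | treat | treat | silent | treat |
| 3.7 | silent | treat | do not treat | conflict |
| 3.8 | silent | treat | do not treat | conflict |
| 3.9 | silent | silent | do not treat | no treatment |

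There is no conflict at 3.9, because item 3.3 requires a value below it.

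**Step 3. Ask what the insulin and exercise triggers add.** At 3.6 or below, item 3.2 already requires treatment. At 3.7–3.8 with a downward arrow, the arrow alone is enough under item 3.3. In a child without symptoms, the insulin and exercise triggers therefore matter only at 3.7–3.8 without a downward arrow, that is, with stable or rising glucose. Item 3.4, taken literally, cancels the stable case.

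**Step 4. Try the 'and' of Section 8.** If all three triggers had to be present, item 3.3 would require a downward arrow, which contradicts a stable trend, and the overlap would be empty. But this works only by withdrawing insulin or exercise as a trigger in its own right. That disagrees with Section 4 item 3.3, the Section 6 table and the questionnaire.

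**Step 5. Size of the delay if item 3.4 is followed literally.** Treatment waits for 3.6 mmol/L unless an arrow or symptoms come first.

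- From 3.7: 3.7 − 3.6 = 0.1 mmol/L lower.
- From 3.8: 3.8 − 3.6 = 0.2 mmol/L lower.

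**Step 6. Test the repair.** With *unless 3.1 or 3.3 applies* added, item 3.4 becomes: 3.7 ≤ *g* ≤ 3.9, stable, no symptoms, and item 3.3 not met. This cannot hold together with item 3.3, so the overlap is empty.

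**The case against.** The best reply is that the intent is already clear. Items 3.1 to 3.3 each open with 'Always', while item 3.4 comes last and uses the softer 'should not', so it can be read as covering whatever is left. The Section 6 table, which defines the treatments, lists the insulin and exercise triggers and omits the prohibition. Section 8 introduces them as an exception to the 3.6 threshold. This stands as evidence of intent, and it is why the repair is a clause and not a redesign. It does not amend item 3.4, which remains an unqualified instruction in the list of operative rules, and the 'and' in Section 8 pulls the other way.

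Four stronger readings are tempting and not supported.

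- A reader might infer that item 3.4 also tells families to withhold treatment from a child with symptoms. Item 3.1 applies whatever the glucose value, and that wording already overrides a rule tied to a glucose band.
- A reader might infer that, with the low notification at 3.6, families have only these written rules to go on at 3.7–3.8. Hypoglycaemia education is reviewed at Visit 1, Section 8 says that families are taught to decide with trend arrows, and the team is in contact every week.
- A reader might infer that adherence cannot be assessed. Section 6 says that "weekly contacts will be made by the research team to monitor adherence", but the diary fields named in Section 4 are glucose, time and treatment. They do not include insulin or exercise, so they could not pick out these episodes even with perfect wording. All enrolled participants are analysed in any case. The consequence for adherence is slight.
- A reader might express the delay as a share of the distance to 3.0 mmol/L. That would be one or two display steps over a small denominator, and it does not measure risk.

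**Conclusion.** The contradiction is real and narrow. It concerns a stable closed-loop child at 3.7 or 3.8 mmol/L with active insulin or exercise, for whom item 3.3 says treat and item 3.4 says do not. Other sections show that item 3.3 was meant to prevail, but item 3.4 is wrong as written.

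The worst consequence is treatment at a value 0.1 to 0.2 mmol/L lower, in a child with stable glucose and no symptoms. Symptoms, a new arrow, the 3.6 threshold with its alert, the urgent-low alert and automatic basal suspension all remain as backstops. The protocol does not say how often the situation arises, so no frequency or harm is claimed. The sample size rests on the margin, the standard deviation and the error rates, none of which depends on this rule, so power is unaffected.

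It should still be corrected, because it is an operative treatment rule for children, it sits in the only band where the two thresholds differ, and its literal form cancels a mitigation on which Section 8 relies. The conclusion assumes readings to 0.1 mmol/L and the 'or' reading of item 3.3, which the Section 6 table and the questionnaire share.

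**What to change.** 1. Section 4, item 3.4: add *unless 3.1 or 3.3 applies*. Naming 3.1 costs nothing and makes explicit what that item already implies.
2. Section 8, Risks and benefits, item 2: join the triggers with 'or', and describe exercise as item 3.3 does, so that it covers activity under way as well as activity just finished.
3. School management plan: Section 4, item 5 says "All participants will be provided an updated school management plan" for the revised phase. Make sure that it carries the same wording as the corrected item 3.4. The plan is not among the documents, so it may already do so.

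The cost is one clause, one aligned sentence and a check of the school plan. No visit, procedure or analysis changes.

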Data identification

The identification of any data to be recorded directly on the Case Report Forms (CRFs) (i.e. no prior written or electronic record of data), and to be considered to be source data.

5 Source and Selection of Participants

Source of Participants

This study aims to recruit children living with T1D and attending the Diabetes Clinic at PCH. Currently, there are approximately 1200 children and adolescents with diabetes, residing in Western Australia with 60% on insulin pump therapy and an increasing number of children on AHCL (n~400) as standard care.

Patients with T1D who satisfy the inclusion criteria, and consented to be contacted for research purposes, will be identified from the existing clinic database (Western Australian Children's Diabetes Database, WACDD) (HREC 2012051EP) by a Child and Adolescent Health Service employee and invited via email to partake in this study. Information on the study will also be disseminated via clinic newsletter and social media.

Participant inclusion criteria.

1. Diagnosis of Type 1 diabetes
2. 6 to 18 years
3. Duration of diabetes of >12 months (to ensure families have gained experience in managing hypoglycaemia)
4. On advanced closed loop therapy
 - 4.1 for at least 4 weeks and
 - 4.2 using the system optimally for >80% in last 2 weeks.

Participant exclusion criteria.

1. Impaired hypoglycaemia awareness. Self-reported Gold score ≥ 4 (these patients need higher glucose targets). For young children (age 6 to 10 years or if the child is developmentally young to self-report, parent-reported response will be used).
2. Increased time spent in hypoglycaemia as documented on CGM (>2% of time spent < 3.0 mmol/L and/or >6% of time spent < 3.9 mmol/L) for last two weeks
3. Families not willing to try lower cut-off due to fear of hypoglycaemia.
4. Severe hypoglycaemia (coma, convulsion or altered consciousness requiring third party assistance) in last 12 months.
5. Any medical or psychological disease state of the child and/or caregiver that limits capacity to participate in the study.

Participant withdrawal criteria

(a) when and how to withdraw participants from the investigational product/trial treatment; Participants will be informed that they can withdraw from the study at any time. They can do so by contacting the research team.

(b) the type and timing of the data to be collected for withdrawn participant(s); All data for withdrawn participant will be used for analysis.

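### Item 3.4 of the revised-phase rules bars treatment at a stable 3.7–3.9 mmol/L and does not except the cases that items 3.1 and 3.3 say must be treated

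*Protocol*

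**What the plan says.** The rules for the revised phase are in Section 4 of the protocol, in the numbered list for conduct during the study.

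- Item 3.1: treat whenever the child is symptomatic, whatever the glucose level.
- Item 3.2: treat when 3.6 mmol/L is reached.
- Item 3.3: "Always institute hypoglycaemia treatment when sensor glucose < 3.9 mmol/L with downward trend arrows on CGM, there is active insulin on board" after a meal bolus, or during and after exercise.
- Item 3.4: "Hypoglycaemia treatment should not be instituted when sensor glucose is between 3.7 and 3.9 mmol/L and stable glucose levels on CGM" and the child is in closed loop. No 'unless' or 'except' follows.

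Three other places describe the same rule.

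- The Section 6 table lists, for the revised treatment, glucose below 3.9 mmol/L with downward arrows, or when "there is active insulin on board (post meal-bolus) or during and post exercise/activity". Symptoms are a separate reason to treat. The table has no do-not-treat rule.
- Section 8, Risks and benefits, item 2, offers as mitigation that "treatment of glucose level < 3.9 mmol/L is recommended if there are downward trend arrows on sensor, active insulin on board and precedent activity/exercise".
- Item 5 of the questionnaire on glucose thresholds (Appendix 3) asks about situations for treating below 3.9 mmol/L other than downward arrows, a post-meal bolus or exercise. It takes those three as known reasons to treat.

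Item 5 of the same Section 4 list adds: "All participants will be provided an updated school management plan, when on the revised hypo Rx phase of the study".

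**The concern.** This rule is the intervention. Whoever decides whether to give glucose at 3.7 or 3.8 mmol/L has to know which instruction applies, and for some children items 3.3 and 3.4 point in opposite directions. The low alert is set "in accordance with the glucose threshold of the study arm", which Section 8 gives as 3.6 mmol/L in the revised phase. It will not have sounded at 3.7–3.8, so the decision rests on the rule as the family or school understands it.

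Two things are at stake. The first is safety: a child with insulin still acting, or just after exercise, is the child for whom Section 8 relies on earlier treatment. The second is clarity about what was tested: a family following item 3.4 to the letter would be using a different treatment rule from the one in the Section 6 table.

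**Working it through.** The plan gives no figure on this point, and the sample size is not involved. The check is to apply items 3.1, 3.3 and 3.4 to each situation in which item 3.4 might apply.

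| Sensor glucose 3.7–3.8 mmol/L, in closed loop | Items 3.1 and 3.3 | Item 3.4 | Result |
|---|---|---|---|
| Stable, no symptoms, no active insulin, no exercise | silent | do not treat | consistent |
| Stable, active post-meal insulin | treat (3.3) | do not treat | conflict |
| Stable, during or after exercise | treat (3.3) | do not treat | conflict |
| Stable, symptomatic | treat (3.1) | do not treat | conflict |
| Downward arrows | treat (3.3) | does not apply, not stable | consistent |

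1. **Range.** Item 3.3 applies below 3.9 and item 3.4 from 3.7 to 3.9. With readings to one decimal place they overlap at 3.7 and 3.8. Item 3.1 has no glucose limit, so for a symptomatic child the conflict covers all of 3.7–3.9.

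2. **Are the conditions in item 3.3 alternatives?** Items 3.3 and the Section 6 table join them with 'or', and the questionnaire also lists them with 'or'. Only Section 8 uses 'and'. If all three conditions were required together, a stable reading could never satisfy item 3.3 and that conflict would vanish. So would most of the mitigation that Section 8 describes. The conflict with item 3.1 would remain on either reading.

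3. **Is precedence stated?** No section says whether item 3.3 or item 3.4 governs.

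4. **Which is intended?** Treatment. The Section 6 table lists the conditions as reasons to treat and contains no prohibition, the questionnaire takes them as settled, and items 3.1 to 3.3 are each worded as absolute. Item 3.4 is therefore the text to correct.

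**The case against.** The strongest reply is that a sensible reader resolves this unaided. Items 3.1 to 3.3 come first and are absolute. Item 3.4 comes last, in weaker terms, and reads naturally as the case left over once the others are excluded. The table and questionnaire agree with that reading. This is a fair account of the intent, and it is why the point is about wording and not a flaw in the design. It does not make item 3.4 correct: an unqualified prohibition beside an absolute instruction should not need two other sections to interpret it.

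Other safeguards also stand: treatment whenever symptomatic (though item 3.4 omits to say so), the 3.6 and urgent-low alerts, closed-loop suspension of basal insulin, the advice on glucose levels for exercise and driving (item 6 of the list), the education review at Visit 1, and weekly contact that monitors adherence, with review if time below 3.0 mmol/L doubles from baseline or exceeds 1%.

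A reader might infer three stronger things that the documents do not support.

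- **That schools are working from the faulty wording.** The protocol says only that an updated plan is supplied; its text is not shown.
- **That the exposure can be put in hours**, starting from the exclusion limit of ">6% of time spent < 3.9 mmol/L". That limit applies to two weeks of screening and covers every level below 3.9. The share that is stable, at 3.7–3.8 and accompanied by insulin or exercise is not given, and nothing links such time to time below 3.0 mmol/L.
- **That the predictive low alert is a similar error**, because item 2.3 leaves it "as per choice of family". That is a stated, deliberate choice, open in both periods. Fixing it would be a debatable trade-off, and the protocol shows no direction or size of bias.

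**Conclusion.** Wrong as written, of advisory severity. Item 3.4 contradicts item 3.3 for a stable 3.7–3.8 mmol/L with active post-meal insulin or around exercise, and item 3.1 for a symptomatic child. It does not contradict the downward-arrow condition. Taken literally, it withholds treatment that the protocol elsewhere intends and counts as mitigation.

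How often this would arise cannot be estimated from the protocol, and no effect on the primary outcome is claimed. The conclusion rests on reading the item 3.3 conditions as alternatives, which Section 4, Section 6 and the questionnaire support. For the symptomatic child it holds on any reading.

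**What to change.** - **Item 3.4:** add 'and no condition in 3.1 or 3.3 is present'. This brings it into line with the Section 6 table.
- **Family instructions and school management plan:** check that both carry the corrected rule, and reissue any that do not.
- **Section 8, Risks and benefits, item 2:** join the conditions with 'or', as in Sections 4 and 6.

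The cost is one clause, one word and a check of two documents, with reissue if needed. It adds no participants, visits or data items, and the intended intervention does not change.

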1.2.2 Worry scale

Below is a list of things that young people with diabetes sometimes worry about concerning low blood sugars.

Circle the number that best describes YOU

	0=NEVER	1=RARELY	2=SOMETIMES	3=OFTEN	4=ALMOST ALWAYS
11 Not recognizing that my blood sugar is low	0	1	2	3	4
12 Not having food, fruit, or juice with me when my blood sugar gets low	0	1	2	3	4
13 Feeling dizzy or passing out in public because of low blood sugar	0	1	2	3	4
14 Having a reaction while asleep	0	1	2	3	4
15 Embarrassing myself because of low blood sugar	0	1	2	3	4
16 Having a reaction while I am by myself	0	1	2	3	4
17 Looking "stupid" or clumsy in front of other people	0	1	2	3	4
18 Losing control because of low blood sugar	0	1	2	3	4
19 No one being around to help me during a reaction	0	1	2	3	4
20 Making a mistake or having an accident at school	0	1	2	3	4
21 Getting in trouble at school because of something that happen when my sugar is low	0	1	2	3	4
22 Having seizures	0	1	2	3	4
23 Getting long term complications from low blood sugar	0	1	2	3	4
24 Feeling dizzy or woozy when my blood sugar is low	0	1	2	3	4
25 Having a low blood sugar	0	1	2	3	4

2. ISPAD Hypoglycaemia Management (2022 Guidelines)

3. Questionnaire on Glucose Threshold for Hypoglycaemia

Thank you for participating in the study.

1. Do you believe there is a need to change the current treatment recommendation to treat glucose level < 3.9 mmol/L? If yes, why? If no, why?

2. Do you think we should have one glucose level for hypo treatment for all or should we have this level personalised to the child/family?

3. On a scale of 1-5 where 1 = very easy and 5 = very hard:

Very easy	Easy	Neutral	Hard	Very hard
1 	2 	3 	4 	5 

How comfortable were you with treating hypo at a glucose level \leq 3.6mmol/L mmol/L?

If you scored 3/4/5 (neutral/hard/very hard), can you elaborate?

4. While treating hypo at a glucose level \leq 3.6mmol/L, did you feel that you/your child spent more time below 3 mmol/L?

5. Were there any other situations, other than downward CGM arrows, post meal insulin bolus or exercise that you would do a hypo treatment for glucose < 3.9 mmol/L.

6. Any other comments?

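### Item 3.4 of the revised-arm rules (do not treat a stable 3.7–3.9 mmol/L) has no exception for item 3.3, so a child with active post-meal insulin or around exercise gets opposite instructions at 3.7–3.8

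*Protocol*

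**What the plan says.** The revised-arm rules stand in Section 4 of the Protocol, in the list of what happens during the study.

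- Item 3.1: "Always institute hypoglycaemia treatment when symptomatic (irrespective of blood/sensor glucose levels").
- Item 3.2: always treat at the revised threshold of 3.6 mmol/L.
- Item 3.3: always treat below 3.9 mmol/L if there are downward arrows, or if "there is active insulin on board (post meal-bolus) or during and post exercise/activity".
- Item 3.4: "Hypoglycaemia treatment should not be instituted when sensor glucose is between 3.7 and 3.9 mmol/L and stable glucose levels on CGM", with the further condition that the child is in closed loop. The item has no exception clause.

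Other places bear on the same rule.

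- The Section 6 treatment table gives, as a revised-arm trigger, "Glucose < 3.9 mmol/L with downward trend arrows on CGM, there is active insulin on board (post meal-bolus) or during and post exercise/activity". It has no do-not-treat row.
- Section 8, Risks and benefits, item 2 offers treatment below 3.9 mmol/L under these conditions as one of two mitigations of the risk of more time below 3.0 mmol/L.
- Question 5 of the threshold questionnaire (Appendix 3) asks about situations "other than downward CGM arrows, post meal insulin bolus or exercise that you would do a hypo treatment" for below 3.9 mmol/L, so it takes those three as known reasons to treat.

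**The concern.** Items 3.3 and 3.4 can both apply to the same child at the same moment and they give opposite orders. Item 3.4 is the protocol's only explicit instruction to withhold glucose. Taken alone, it withdraws a safeguard on which Section 8 relies, in two situations where glucose may soon fall.

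The device does not settle the matter. In the revised phase the low alert is set at 3.6 mmol/L and predictive low alerts are optional. At a steady 3.7 or 3.8 the low alert does not sound, and the family depends on the written rule.

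Two other users need a single rule. In the revised arm "weekly contacts will be made by the research team to monitor adherence and hypoglycaemia events", and treating a steady 3.7 with active insulin obeys 3.3 while breaking 3.4. Schools need it too: "All participants will be provided an updated school management plan, when on the revised hypo Rx phase of the study".

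**Working it through.** The plan gives no figure on this point, so the check is one of logic.

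**Where the arms differ.** The standard arm treats below 3.9 mmol/L, which is 3.8 or lower if the display has one decimal (an assumption). The revised arm always treats at 3.6 or lower. The thresholds therefore differ at 3.7 and 3.8 only.

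**Items 3.2 to 3.4 applied to a child with stable glucose, in closed loop, without symptoms:**

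| Sensor glucose (mmol/L) | No active insulin, no exercise | Active insulin, exercise, or both |
|---|---|---|
| 3.6 | treat (3.2) | treat (3.2, 3.3) |
| 3.7 | do not treat (3.4) | treat (3.3) and do not treat (3.4) |
| 3.8 | do not treat (3.4) | treat (3.3) and do not treat (3.4) |
| 3.9 | do not treat (3.4) | do not treat (3.4) |

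At 3.9 there is no clash, because 3.3 needs a value below 3.9. At 3.7 and 3.8 there are 2 × 4 = 8 combinations of value, insulin (yes or no) and exercise (yes or no). The clash occurs in 2 × 3 = 6 of them. This counts logical cases and says nothing about how often they arise.

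**Count by trigger.** Apart from the 3.6 threshold, the revised arm has four triggers.

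1. Symptoms: no real conflict. Item 3.1 applies whatever the sensor shows, so it already overrides a rule defined by a sensor-glucose band.
2. Downward arrows: no conflict. Item 3.4 requires stable glucose.
3. Active post-meal insulin: conflict with 3.4.
4. Exercise: conflict with 3.4.

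So 4 − 2 = 2 triggers collide.

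**Does another passage settle it?** Item 6 of the same list tells participants to "maintain optimal glucose levels as per recommendations for exercise and driving". It does not say whether a steady 3.7 or 3.8 is treated, so it leaves the question open.

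**Statistical inputs.** The sample size rests on the margin of 0.56, the standard deviation of 0.96, 36 evaluable participants and a one-sided alpha of 0.025. None of these derives from item 3.4.

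**The case against.** The best answer is that the intent is plain. Items 3.1 to 3.3 all open with *Always*, whereas 3.4 says only *should not* and comes last. The Section 6 table lists active insulin and exercise as triggers with nothing against them. Section 8 item 2 presents the same conditions as exceptions to the revised threshold, and the questionnaire takes them for granted. Safeguards also remain: treatment at 3.6 or lower in every case, the urgent-low alert always on, education reviewed at Visit 1, families with more than 12 months' experience of diabetes, and weekly contact.

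This stands as far as it goes. It shows that 3.3 is meant to prevail and it keeps the point minor. It does not remove the clash, because a reader must assemble the rule from several sections, while 3.4 in the instruction list still says the opposite without qualification.

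It is also true that no adherence metric is set and no analysis based on adherence is stated. The adherence consequence is therefore limited to the judgement made at the weekly contacts, although Trial Termination in Section 4 does list non-adherence among the criteria for a participant's continuing in the study.

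A reader might go further and infer that symptomatic children are told not to treat. Item 3.1 rules that out. A reader might also infer that families are in fact receiving conflicting advice. The school plan and family materials are not shown, so this is unknown.

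**Conclusion.** The point holds for item 3.3 against item 3.4. With active post-meal insulin, or during and after exercise, a stable 3.7 or 3.8 mmol/L in closed loop attracts opposite instructions. That is two of the four triggers other than the threshold, at two displayed values, and it rests on the assumption of a one-decimal display. It is a minor but safety-relevant wording error in the rule that defines the intervention.

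Because the clash lies where the arms differ, one might suppose that it biases the comparison of time below 3.0 mmol/L. The document does not support that. It gives no frequency for these situations and no evidence of how families resolve them, and the intended reading can be recovered. No sample size, margin or analysis is affected.

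**What to change.** Begin item 3.4 with *Unless 3.1 or 3.3 applies,* and leave the rest of the item as it is. Naming 3.1 is for completeness, since that item already prevails. Check that the school plan and family materials state the same rule, and judge adherence at the weekly contacts against it.

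As an editorial matter only, Section 8 item 2 joins the three conditions with *and* where item 3.3 and the Section 6 table use *or*; changing it to *or* would align them. That sentence describes risk mitigation and forbids nothing.

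The cost is a wording amendment and a check of materials already issued. Design, sample size and analysis stay as they are.
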